8.5. Concomitant medication documentation

All concomitant medications and supplements will be recorded from the time of informed consent through protocol Day 28. There are no known drug-drug interactions.

Concomitant medications will be collected directly in REDCap though a link embedded in the eMocha app. Participants will include their eMocha app username and cell phone number on the survey. For participants who are unable to access or use eMocha, surveys will be interviewer administered over the phone by trained research staff.

8.6. Pregnancy Test

All participants will be asked to provide information determining childbearing status. Females who are post-menopausal (absence of menses for 12 months or greater) or who have had a hysterectomy are considered not to be of childbearing potential. Any females not meeting these criteria are considered to be of childbearing potential and will have a dipstick urine HCG test performed at the point of care at screening. Pregnant women will not be enrolled in this study.

Females of childbearing potential will be cautioned against getting pregnant or attempting to get pregnant during this study. Requirements for ongoing contraception are noted in protocol section 6.1.1.6.

8.7. Vital Signs

Complete Vital Signs: Temperature, Pulse, Respiratory Rate, Blood Pressure and Pulse Oximetry will be collected at the study site after at least 3 minutes of rest.

Limited vital signs (Temperature, Respiratory Rate, and Pulse Oximetry [when available]) will be performed after 3 minutes of rest at the participant's home using study supplies and documented by EmoCha software, or other HIPAA-compliant method of remote contact. Readings will be taken at least once a day. Participants who have a SpO₂ reading of <95% or respiratory rate >25 breaths per minute after at least 3 minutes of rest will be asked to take a confirmatory measurement and instructed to visit an emergency room.

8.8. Physical Examination

A limited physical examination will be performed to examine the following body systems: Constitutional; HEENT; Cardiovascular; Pulmonary; Gastrointestinal; Skin; and Musculoskeletal. Abnormal findings will be evaluated for clinical significance toward an assessment of eligibility, treatment-emergent adverse events, and assessment of COVID-19 signs and symptoms.

8.9. Randomization

Randomization will take place on day 0 after screening activities have been performed and the Investigator or designee has determined that the participant is eligible. Day 0 laboratory tests including blood SARS-CoV-2 RT-PCR results are not part of the eligibility criteria and participants will be randomized without this information. Randomization will be built into the study REDCap database. It will not be known at entry/screening whether participants are part of Group A or Group B since their COVID-19 infection status will not be known until entry/screening specimens are processed. All participants will be randomized in a 1:1 ratio to receive Lambda/Lambda (Arm 1) or Placebo/Placebo (Arm 2). Participants who are not eligible for enrollment into Step 2 (will be removed from protocol therapy Single dose of Lambda or placebo) respectively.

8.10. Drug/Placebo Administration

Peginterferon-Lambda-1a 180 mcg or dummy placebo injection will be administered subcutaneously by personnel on Day 0. Participants will be sent home for self-monitoring and will communicate with study staff between in-person visits to communicate any adverse events.

Details on drug/ placebo intervention and storage are in Protocol Section 9.

8.11. Upper respiratory specimens for SARS-CoV-2 assessment

All participants in Group A Prevention cohort with onset of symptoms consistent with COVID-19 will be referred for clinical testing of upper respiratory samples for evidence of SARS-CoV-2.

All persons who remain asymptomatic will have study testing with upper respiratory samples for evidence of SARS-CoV-2 at study day 7, 14, and 28. When onsite visit for Day 28 is not on the exact Day 28, the study team will make every effort to have the upper respiratory specimens self-collected Day 28 at the participant's residence.

Specimens obtained will depend on site of collection and availability of swabs. Mid turbinate samples will be collected using a nylon flocked swab using the following steps: 1) inserting the swab into the nose in the horizontal position until gentle resistance is met, 2) leaving the swab in for 10-15 seconds then, rotating the swab, 3) repeating in the other nostril with the same swab. Specimens collected with nasopharyngeal swabs will be done according to standard instructions. The swab will be inserted into the nostril parallel to the palate. The swab should reach a depth equal to the distance from nostrils to outer opening of the ear. The swab will be left in place for several seconds to absorb secretions. The swab will be slowly removed from the nostril while rotating it.

8.12. Serology for SARS-CoV-2

At entry and day 28, all participants will have blood sampled to detect antibodies against the SARS-CoV-2 spike protein (S1 subunit). Testing will be performed at the Johns Hopkins Pathology Laboratory using the commercial Euroimmun antibody assay according to the manufacturer's recommendation. This assay has been validated by the Johns Hopkins laboratory. 6 mL of blood will be collected for each timepoint.

8.13. CBC and CMP

Complete blood count and comprehensive metabolic panel will be collected and tested for safety assessment at day 0. 12 mL of blood will be collected at each timepoint.

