Interleukin (IL)-29 is a member of the Type III interferon (IFN) family. Lambda targets type III IFN receptors which are distinct from the type I IFN receptors targeted by interferon alfa. Lambda type III receptors are highly expressed in epithelial cells within the lungs, intestine, and liver with limited expression on hematopoietic, muscle, and central nervous system cells, which may reduce the off-target effects associated with other interferons and has demonstrated improved tolerability with Lambda treatment [6]. Peginterferon lambda-1a (Lambda) is a conjugate of recombinant human interleukin 29 (rIL-29) and a linear polyethylene glycol (PEG) chain, which enables once a week dosing. Lambda has been evaluated in Phase 1, 2 and 3 clinical trials in over 3,000 healthy volunteers and patients infected with chronic hepatitis B virus (HBV) and chronic hepatitis C virus (HCV) [7]. In randomized controlled trials of interferon lambda-1a and interferon alfa-2a for the treatment of chronic HCV and HBV infection, interferon lambda-1a demonstrated similar antiviral efficacy and improved tolerability compared to interferon alfa-2 with lower frequency of hematologic suppression. However, in August 2014, the development of interferon lambda-1a was terminated due to the advent of HCV direct acting antiviral therapy and remains under investigation for treatment of hepatitis D virus (HDV) infection [8].

Interferon alfa has been evaluated in a study of 22 patients with the 2002-2003 SARS-CoV infection who received corticosteroids alone or in combination with interferon alfa. Interferon alfa was associated with more rapid resolution of lung radiographic abnormalities, less need for supplemental oxygen, and lower levels of creatine kinase [9]. In animal models, interferon lambda inhibits replication of respiratory viruses such as influenza as well as the SARS-CoV and may induce resistance of the respiratory epithelium to viral infections. Lambda interferons are a major

component of the innate immune defense to viruses, bacteria, and fungi. Lambda has been shown to protect against pulmonary influenza and human metapneumovirus (HMPV), gastrointestinal rotavirus and norovirus, and hepatic HBV, HCV and HDV [10]. Studies in mice have shown potent antiviral effects of Lambda against influenza and SARS coronavirus, rotavirus, norovirus, and reovirus [11].

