8.1. COVID-19 Symptom Screen

The spectrum of clinical presentation for SARS-CoV2 can range from asymptomatic infection, mild symptomatic infection, or severe symptomatic infection with an acute respiratory distress syndrome. Presenting symptoms compiled from hospitalized patients include fever (44-99%), cough (59-82%), myalgias (11-44%), fatigue (>35%), sore throat (<20%), nausea/vomiting/diarrhea (3-10%), headache (<10%), and rhinorrhea (<5%) [14-17]. The symptoms screen will incorporate the CDC recommendations including: fever, cough, shortness of breath, chills, muscle pain, new loss of taste or smell, vomiting or diarrhea, and/or sore throat.

Participants will be contacted by telephone and screened for these symptoms consistent with COVID-19 at prescreening. Individuals who do not endorse symptoms will be instructed to present to the ambulatory testing facility with appropriate precautions including physical distancing and masking. Persons who are not able to travel to/from the site in a manner consistent with recommendations will not be enrolled. At subsequent visits, participants will complete this symptom screen electronically using Eموcha Mobile Health or other HIPAA-compliant means of remote contact.

Eموcha Mobile Health (<https://www.emocha.com>) is a pioneering mobile health company with experience in clinical trials, population health management, and customized clinical applications with a proven track record for remote and mobile health research data collection. Eموcha is a HIPAA compliant commercial mobile health software platform for remote patient monitoring. If the participant is not able to use this technology, the study team will use alternative communication include telephone and secure video connection such as Doximity or other compliant platform.

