8.4. Administration of Flu-PRO Questionnaire

Participants will be assessed to determine the presence or absence of symptoms consistent with COVID-19 using the CDC defined COVID-19 symptom check list daily. In addition, Flu-PRO, a validated, standardized patient-reported outcome (PRO) symptom scale that comprehensively assesses the symptom experience in acute respiratory symptoms across multiple body systems will be used at enrollment and days 1-14 and 28. This will provide an opportunity to assess for potential symptoms related to Lambda as well as COVID-19.

For remote visits, FLU-PRO will be collected directly in REDCap through a link embedded in the

eMocha app. Participants will include their eMocha app username and cell phone number on the survey. For participants who are unable to access or use eMocha, surveys will be interviewer administered over the phone by trained research staff.

A validated, standardized patient-reported outcome (PRO) symptom scale that comprehensively assesses the symptom experience in influenza across multiple body systems was reported in 2016 by Powers and colleagues at the National Institute of Allergy and Infectious Diseases [18]. The purpose of the InFLUenza Patient-Reported Outcome (FLU-PRO[©]) measure is to comprehensively assess the presence and severity of influenza symptoms across body systems often affected by these viruses. The instrument was created in accordance with drug development recommendations of the US Food and Drug Administration (FDA) [19]. This new instrument yields a profile of scores across six body systems with a total score reflecting overall symptom severity. The questionnaire instructs respondents to rate the severity of 37 influenza symptoms over the past 24 hours, including those related to the nose, throat, eye, chest, head, stomach, fatigue, and body aches/pains. Six items measured the same symptom using different wording in order to select the best performing item for the final instrument. For 32 of 37 items, respondents rated the severity of each symptom on 5-point Likert-type scales from 0 (“Not at all”), 1 (“A little bit”), 2 (“Somewhat”), 3 (“Quite a bit”), to 4 (“Very much”). For the five remaining items, severity is expressed as frequency of occurrence: vomiting or diarrhea (0 times, 1 time, 2 times, 3 times, or 4 or more times), and sneezing, coughing, and coughed up mucus or phlegm on a scale from 0 (“Never”) to 4 (“Always”), with higher scores indicating more severe symptoms.

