8.15. Adverse Event Evaluation

An AE is any untoward medical occurrence in a clinical study participant administered a medicinal (investigational or non-investigational) product. An AE does not necessarily have a causal relationship with the intervention. An AE can therefore be any unfavorable and unintended sign (including an abnormal finding), symptom, or disease temporally associated with the use of a medicinal (investigational or non-investigational) product, whether or not related to that medicinal (investigational or non-investigational) product (Definition per ICH).

This includes any occurrence that is new in onset or aggravated in severity or frequency from the baseline condition, or abnormal results of diagnostic procedures, including laboratory test abnormalities.

All adverse events, both serious and nonserious, will be collected from the time of informed consent through protocol Day 28. Participants will be asked open-ended and non-leading questions to evaluate for adverse events. Participants will also be asked directed questions to evaluate the presence or absence of fever, chills, arthralgia, myalgia, or pain. To monitor for injection site reactions, participants will be asked directed questions regarding pain, erythema, induration, or pruritus. The injection site will be inspected via video check-in on Day 7.

Adverse events will be collected directly in REDCap though a link embedded in the eMocha app. Participants will include their eMocha app username and cell phone number on the survey. For participants who are unable to access or use eMocha, surveys will be interviewer-administered over the phone by trained research staff.

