Participants who are found to be infected with SARS-CoV-2 at baseline (Group B) or who become infected during the course of the study (Group A) will not return to the study site until Day 28 or until criteria for discontinuation of infected status is met per HEIC standards, whichever occurs later. In the event that an interim in-person visit is required to evaluate an adverse event, these participants may be seen in an ambulatory setting equipped for encounters with SARS-CoV-2 infected persons. In the event that participants become hospitalized, study evaluations that coincide with clinical care will be abstracted from the medical record. Research-specific evaluations will not continue in the inpatient setting.

11. Risks and Benefits

Potential Risks of Treatment

Identified risks associated with treatment with Lambda based on nonclinical and/or clinical data, as well as potential class effects, include hepatobiliary toxicity (transaminase elevations with or without hyperbilirubinemia) and injection site reactions; potential risks include neuropsychiatric disorders (including depression), cardiovascular events, immunogenicity/hypersensitivity reactions, autoimmune disorders, elevated amylase/lipase, dermatitis, hypersensitivity reaction, injection site reaction, and reproductive risk. Complete information on preclinical and clinical safety data is located in the Investigator Brochure.

Potential Benefits of Participation

Potential benefits include prevention of infection with SARS-CoV-2 infection or reduction in severity of COVID-19 symptoms. It is not yet known whether Lambda will have any benefit in this population.

Alternatives to Participation

The alternative to participation in this study is routine care and monitoring following close contact with an individual with COVID-19.

12. Outcome measures

12.1 Group A Prevention cohort primary endpoint:

- No evidence of SARS-CoV-2 infection at or before study day 28

For the purpose of the study endpoint, SARS-CoV-2 infection is defined as any of the following outcomes:

1. SARS-CoV-2 detected in upper respiratory samples at any of day 7, day 14 or day 21; or
2. New finding of serum antibodies (IgA or IgG) against the SARS-CoV-2 spike protein according to validated specifications and performance characteristics at or prior to day 28.

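### The metabolic panel is drawn only on the day of dosing, so a silent transaminase or bilirubin rise, an identified Lambda risk, has no scheduled test afterwards

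*Combined protocol and SAP*

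**What the plan says.** Section 8.13 gives one time for the blood count and chemistry: "Complete blood count and comprehensive metabolic panel will be collected and tested for safety assessment at day 0". The same section gives a 12 mL volume for each timepoint but names no second timepoint. Section 9.2 places the single injection on Day 0 as well.

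Section 11 separates identified from potential risks. The identified risks "include hepatobiliary toxicity (transaminase elevations with or without hyperbilirubinemia) and injection site reactions". For the injection site, section 8.15 provides directed questions and an inspection: "The injection site will be inspected via video check-in on Day 7".

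The AE definition in section 8.15 covers changes from baseline "or abnormal results of diagnostic procedures, including laboratory test abnormalities". On the collection period it says: "All adverse events, both serious and nonserious, will be collected from the time of informed consent through protocol Day 28".

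The synopsis makes the proportion with treatment-emergent AEs a secondary outcome in both cohorts. Section 13.2.2 treats AE data as mainly descriptive, with arm comparisons of SAEs and of Grade 3 or higher events. Section 8.12 requires blood from all participants at entry and at Day 28, for antibody testing.

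**The concern.** Of the two identified risks, the one visible on the skin has an active check after dosing. The one defined by laboratory values has none. A sample taken on the day of injection cannot show a delayed effect of a pegylated product that section 4 describes as suited to weekly dosing. The Day 0 panel is not a screening test either, since section 8.9 says Day 0 laboratory tests are not part of eligibility. It is a baseline with nothing scheduled to compare it with.

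The AE definition includes laboratory abnormalities, but scheduled testing after dosing cannot produce a hepatic one. The AE proportions by arm would omit silent hepatic events unless one turned up by chance, and the plan does not say so. Section 13.1 expects about 110 of 164 participants to be uninfected at entry, and section 11 says benefit is not yet known. Tolerability therefore carries weight in the overall judgment.

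**Working it through.** The plan states no figure on this point, so there is none to reproduce. The check has two parts.

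**1. Counting scheduled panels after dosing.**
- Section 8.13: Day 0 only. The reference to each timepoint adds no day.
- Section 8.12: blood at entry and Day 28, tested for spike antibodies.
- Section 8.14: exploratory blood, with no liver chemistry.
- Section 8.15: directed questions on fever, chills, joint and muscle pain, other pain and the injection site. None is hepatic.
- Section 14: AE review and an independent monitoring board, with no laboratory schedule.

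The count is one panel at Day 0 and none later, in either cohort. This rests on the text. In the extracted tables, 7.2 lists the CBC and CMP row with no mark and 7.3 has no such row. Their Day 28 columns are too incomplete to prove anything, because they also lack the Flu-PRO and respiratory samples that sections 8.4 and 8.11 require on that day.

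**2. What a Day 28 panel could find.** From section 13.1, 164 randomized 1:1 gives 164/2 = 82 on Lambda. Let r be the proportion with an elevation after the dose and f the fraction of elevations still present at Day 28. The documents give neither, so both are assumptions: r from 2% to 5% and f from 5% to 100%. Then

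P(at least one case) = 1 − (1 − r·f)^82.

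| f | r = 2% | r = 5% |
|---|---|---|
| 5% | 7.9% | 18.6% |
| 10% | 15.1% | 33.7% |
| 25% | 33.7% | 64.4% |
| 50% | 56.1% | 87.5% |
| 100% | 80.9% | 98.5% |

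At the low corner, 1 − (1 − 0.001)^82 = 0.079. At the high corner, 1 − 0.95^82 = 0.985. Expected cases (82·r·f) run from 82 × 0.02 × 0.05 = 0.08 to 82 × 0.05 × 1 = 4.1.

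If 10% are not sampled, 82 × 0.9 ≈ 74 remain and the range becomes 7.1% to 97.7%.

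If no case is seen, the one-sided 95% upper bound is 1 − 0.05^(1/82) = 3.6%, or 1 − 0.05^(1/74) = 4.0% with 74 sampled. This bounds only the rate of elevations still present at sampling.

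**The case against.** **Other routes exist.** Section 8.4 says of Flu-PRO: "This will provide an opportunity to assess for potential symptoms related to Lambda as well as COVID-19". The symptom screen in section 8.1 covers "fever, cough, shortness of breath, chills, muscle pain, new loss of taste or smell, vomiting or diarrhea, and/or sore throat". Open AE questions and clinical care add to these. They may bring a symptomatic hepatic event to light, so it would be wrong to infer that hepatic events go wholly undetected. But the routes are nonspecific and cannot show an elevation without symptoms.

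**One dose, a descriptive analysis and a known drug.** Dosing is single, section 4 cites more than 3,000 people in earlier trials, and section 11 defers to the Investigator Brochure for full safety data. How much follow-up chemistry one dose needs may depend on that source, which was not available here. This stands, and it is a reason to keep the severity low.

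**Few contacts by design.** Section 10 says the protocol aims to reduce touchpoints, and infected participants stay away from the site until Day 28 or later. That is a fair reason for having no early panel. It does not explain leaving the panel off a blood draw that is already planned.

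**Is that draw really planned for everyone?** The extracted table 7.3 shows no Day 28 serology mark for Group B. Section 8.12 says all participants, and the incomplete Day 28 columns are too weak to contradict it.

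**The fix may find little.** If rises are early and brief, Day 28 comes four weekly dosing intervals (28/7) after the injection and may miss them. This stands.

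**Stronger readings.** A reader might infer that the Grade 3 or higher comparison in section 13.2.2 is materially impaired. The documents do not support that: they give no rate and no grade distribution for hepatic elevations, so no claim about power for that comparison is made. A reader might also extend the point to the blood count. Section 11 lists no hematologic risk, and section 4 reports "improved tolerability compared to interferon alfa-2 with lower frequency of hematologic suppression", so the point is confined to liver chemistry.

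**Conclusion.** The gap is real and clear from the text: after dosing, no scheduled test can detect an asymptomatic transaminase or bilirubin elevation, although section 11 lists it as an identified risk and section 8.15 would count it as an AE. How much is missed cannot be determined from the documents. The 7.9% to 98.5% range depends wholly on the assumed rates and persistence, and shows that a Day 28 panel could find almost nothing or nearly always find something. The point is an optional, low-severity improvement to safety ascertainment. It is not a validity problem and leaves the efficacy analysis untouched.

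**What to change.** - In section 8.13, add a CMP at the Day 28 blood draw of section 8.12 for all participants in both groups, and mark it in schedules 7.2 and 7.3.
- State that an abnormality from this draw is recorded as an AE even if the draw falls after Day 28. The visit window runs to Day 32 (28 + 4), and section 10 lets infected participants return later still, whereas section 8.15 ends AE collection at Day 28.
- In section 13.2.2, report change from Day 0 and CTCAE grade by arm, descriptively. Add that one Day 28 sample may miss early transient rises, so absence of events is not evidence of hepatic safety.

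The cost is at most 12 mL more blood per participant (the section 8.13 volume for count and chemistry together), a routine assay and a table edit. No visit is added. The limitation that remains is the late timing.
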